9.2.5 Clinical Risks and Mitigation Strategy

A number of safety aspects have been built into the design of this study in light of the preclinical and clinical safety data with elenbecestat (E2609), and to mitigate clinical risk in the progression from 14 days of dosing in the MAD study to 18 months of Core Study treatment and 24 months of OLE Phase treatment in this Phase 2 study. (revised per Amendment 07) These safety aspects include the following:

- Immunology-related and infection-related exclusion criteria for both the Core Study and the OLE Phase (revised per Amendment 07)
- Review of unblinded safety data by an independent DSMB at regular intervals
- Safety criteria for study drug discontinuation based on CD4 (T helper cells), CD8 (cytotoxic T cells), CD19 (B cell) during the Core Study and absolute lymphocytes during the OLE Phase (revised per Amendment 07)
- Safety criteria for study drug discontinuation during the Core Study and OLE Phase based on skin rash, reoccurrence of herpes virus infections including any oral herpes, genital herpes or shingles, other infections, MRI changes, ECGs, and pregnancy. (revised per Amendment 07)

In addition to the features above, other safety aspects of this study designed to mitigate clinical risk include the following:

- Blinded safety data will be monitored by Eisai at regular intervals during the course of the study
- Routine safety assessments will include the monitoring and recording of all AEs and SAEs, monitoring of hematology, blood chemistry, and urinalysis, measurement of vital signs, regular ECGs, physical and neurological examinations, and dermatological assessments at regular intervals. (revised per Amendment 07) AEs that might indicate signals of possible drug abuse potential will require a detailed follow-up. Subjects reporting AEs relating to abnormal dreams, nightmares, or sleep terror will be questioned on the frequency and impact of these events. To assess potential immunomodulatory effects, peripheral blood mononuclear cells (PBMCs) will be collected at baseline, during treatment, and posttreatment.

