9.3.3 Removal of Subjects from Therapy or Assessment

The investigator may discontinue study drug or withdraw the subject from the study at any time for safety or administrative reasons. The subject may decide to stop study drug or withdraw from the study at any time for any reason.

Subjects who discontinue taking study drug prematurely for any reason will undergo an ED Visit within 7 days of their last dose of study drug (see [Section 9.1.2.2](#)). Follow-Up Visits will also be scheduled 2, 4, 8, and 12 weeks after the last dose of study drug in the Core Study (see [Section 9.1.2.3](#)), and 4 and 12 weeks after the last dose of study drug in the OLE Phase (see [Appendix 6](#)). (revised per Amendments 04, 05 and 07)

The primary reason for discontinuation and all other reason(s) contributing to the subject's discontinuation from study drug(s) should be collected on the Subject Disposition eCRF page. In addition, the date of last dose of study drug(s) will be recorded on the Study Drug Dosing eCRF page. If a subject discontinues study drug and withdraws from the study at the same time, the ED Visit will be followed (see [Section 9.5.5](#)).

Safety-related criteria for discontinuation of study drug during the Core Study include the following: (revised per Amendments 07)

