- c. Subjects with clinical evidence of infection will have their CD4 (T helper cells), CD8 (cytotoxic T cells), and CD19 (B cells) absolute counts measured. Blood and other biological samples will also be collected for investigations of infective pathogens (eg, serological tests, quantitative polymerase chain reaction, microscopy, and culture) where appropriate. In subjects with infection, if any of their absolute cell counts meets the discontinuation thresholds, study drug will be discontinued. All subjects with severe infections will be discontinued from study drug. All subjects with herpes zoster (shingles) or ocular herpes infections will be discontinued from study drug, regardless of severity of presentation. Subjects with mild or moderate infection may continue treatment with study drug unless otherwise clinically indicated or otherwise specified below. Specifically, when any of the CD4 (T helper cells), CD8 (cytotoxic T cells), and

CD19 (B cells) absolute counts are between the population-adjusted LLN and the discontinuation thresholds, subjects with infections of moderate intensity will be discontinued from study drug (eg, subjects whose infections are not localized, or subjects who are systemically unwell, or who require systemic anti-infective drug treatment). All subjects with infection who are discontinued from study drug will be followed for a period of 12 weeks or until the infection resolves/ stabilizes or until the CD4 (T helper cells), CD8 (cytotoxic T cells), and CD19 (B cells) absolute counts have returned to greater than population-adjusted LLN (whichever comes latest). (revised per Amendments 02 and 04)

Table 2 Study Drug Actions for Lymphocyte Subset Absolute Counts and Infection

| Criterion | Severity of Infection | | | |
|--|--|---|---|------------------------|
| | None | Mild | Moderate | Severe |
| CD4 (T helper cells), CD8 (cytotoxic T cells), or CD19 (B cells) absolute counts below discontinuation threshold | If confirmed with repeat testing within 1 week, then temporarily suspend study drug as per instructions above. | Discontinue study drug | Discontinue study drug | Discontinue study drug |

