| CD4 (T helper cells), CD8 (cytotoxic T cells), or CD19 (B cells) absolute counts between population-adjusted LLN and discontinuation threshold | May continue treatment with study drug unless discontinuation is clinically indicated | May continue treatment with study drug unless discontinuation is clinically indicated | Discontinue study drug | Discontinue study drug |
| CD4 (T helper cells), CD8 (cytotoxic T cells), or CD19 (B cells) absolute counts always > population-adjusted LLN | May continue treatment with study drug unless discontinuation is clinically indicated | May continue treatment with study drug unless discontinuation is clinically indicated | May continue treatment with study drug unless discontinuation is clinically indicated (See (e) for exception) | Discontinue study drug |

LLN = lower limit of normal.

(Table revised per Amendments 02 and 04)

- d. A subject with any skin rash of moderate to severe intensity, or any rash lasting more than 72 hours regardless of severity (see (e) for exception), will be discontinued from study drug and a dermatological consult will be requested regardless of whether the rash is considered drug-related or due to other causes. For cases where the investigator suspects a drug rash, regardless of severity, the subject will be discontinued from study drug, a dermatological consult will be requested, and a skin biopsy will be performed to confirm the diagnosis. The skin rash will be treated as per standard care and will be followed up until resolution regardless of etiology or severity.

- e. Subjects who develop moderate to severe oral or genital herpes should be discontinued from study drug. Subjects who develop a mild case of oral or genital herpes may remain on study drug even if the event lasts more than 72 hours.

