- f. Development of any of the following features on MRI: vasogenic edema, macrohemorrhage, an area of superficial siderosis, or a symptomatic microhemorrhage. If discontinued from study drug, subjects will undergo an ED Visit within 7 days after discontinuation and will attend the Follow-Up Visits 2, 4, 8, and 12 weeks after the last dose of study drug. They will also undertake an Unscheduled Visit (with MRI) at approximately 4 weeks after the visit at which such MRI features were first identified. An MRI will also be performed at approximately the time of the final Follow-Up Visit (Visit 20). Additional visits for safety may be arranged if clinically indicated in the opinion of the investigator, including after 12 weeks after the last dose of study drug. At any time during the treatment period, subjects who have asymptomatic, treatment-emergent microhemorrhages as detected by MRI, but none of the features which merit discontinuation of treatment (ie, vasogenic edema, macrohemorrhage, an area of superficial siderosis, or a symptomatic treatment-emergent microhemorrhage) may continue with treatment. These subjects will have safety assessments (including MRI) at approximately 4 weeks after the visit at which such MRI features were found. They will also continue with the scheduled MRI scans. Additional unscheduled MRI scans may be arranged on an individual subject basis in discussion with the study medical monitor. (revised per Amendment 04)
- g. A postdose ECG with an average QTcF interval >500 msec from triplicate ECGs
- h. A postdose ECG with a QTcF interval increase from baseline >60 msec and a QTcF interval >450 msec as demonstrated from triplicate ECGs
- i. Any seizure (motor or non-motor)
- j. Pregnancy

Safety-related criteria for discontinuation of study drug during the OLE Phase are provided in [Appendix 6](#). (revised per Amendment 07)

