Eligible subjects who choose to participate in the OLE Phase may enter the OLE Phase immediately following the completion of Visit 20 (ie, Visit 21 procedures may be completed on the same day as Visit 20). Subjects who are eligible to participate in the OLE Phase but who do not transition to the OLE Phase on the day of Visit 20 may enter the OLE Phase any time within 4 weeks of Visit 20. The Medical Monitor must be contacted if Visit 21 is to occur more than 4 weeks after Visit 20. For all subjects, assessments performed at V20 may serve as baseline values for the OLE Phase (ie, results of assessments conducted at Visit 21) with exceptions of laboratory assessments and vital signs, which must be repeated if Visit 21 occurs more than 10 days from Visit 20.

During the OLE Phase, subjects will receive open-label elenbecestat (E2609) 50 mg per day for up to 24 months. Subjects with pending INR and serum pregnancy test results (females subjects of child bearing potential only) but who are otherwise qualified may begin OLE dosing at Visit 21; however, these subjects must discontinue study drug treatment immediately if either test result meet the exclusion criteria.

Safety assessments will be performed as described in [Table 14](#). Subjects may discontinue from study drug for any reason. Subjects who complete 24 months of OLE treatment or who discontinue the study drug must comply with the Early Discontinuation Visit (within 7 days after the last dose of study drug) and the Follow-Up Visits (weeks 4 and 12 after the last dose of study drug).

The study will end when the last visit for the last subject has completed the OLE Phase.

Removal of Subjects from Therapy or Assessment

The investigator may discontinue study drug or withdraw the subject from the study at any time for safety or administrative reasons. The subject may decide to stop study drug or withdraw from the study at any time for any reason. Subjects who discontinue study drug prematurely for any reason will undergo an ED Visit within 7 days of their last dose of study drug. Subjects who discontinue from treatment during the OLE will have 2 posttreatment Follow-Up visits at 4 and 12 weeks after the last dose of study drug.

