The primary reason for discontinuation and all other reason(s) contributing to the subject's discontinuation from study drug should be collected on the ED from study drug electronic case report form (eCRF) page (see Protocol [Section 9.5.5](#)). In addition, the date of last dose of study drug will be recorded on the Study Drug Dosing eCRF page.

Safety-related criteria for discontinuation of study drug include the following:

1. Absolute lymphocyte count will be monitored during the study. Should a subject develop lymphocytopenia (less than $800/\text{mm}^3$ or LLN, whichever is higher), a confirmation test should occur as soon as possible but no later than within 5 days with a repeat test of absolute lymphocytes. If confirmed, study drug administration should be interrupted for a minimum period of 2 weeks. Restart of study drug may take place only when absolute lymphocyte count returns to greater than LLN. Absolute lymphocyte count will be measured 4 weeks after restart of study drug. Subsequent measurements of absolute lymphocyte counts will follow the schedule of assessments and any results showing a Grade 2 or greater lymphocytopenia (less than $800/\text{mm}^3$) should be handled as above. If a 2nd occurrence of Grade 2 or greater lymphocytopenia (less than $800/\text{mm}^3$), that is confirmed on repeat testing, occurs within 6 months, then the subject should be discontinued permanently from the study drug.
2. A subject with any skin rash of moderate to severe intensity, or any rash lasting more than 72 hours regardless of severity (with the exception of oral or genital herpes as described in the next paragraph), will be discontinued from study drug and a dermatologic consult will be requested regardless of whether the rash is considered drug-related or due to other causes. For cases where the investigator suspects a drug rash, regardless of severity, the subject will be discontinued from study drug, a dermatologic consult will be requested, and a skin biopsy will be performed to confirm the diagnosis. The skin rash will be treated as per standard care and will be followed up until resolution regardless of etiology or severity.
3. Subjects who develop moderate to severe oral or genital herpes should be discontinued from study drug. Subjects who develop a mild case of oral or genital herpes may remain on study drug even if the event lasts more than 72 hours.

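### Section 9.2.5 says the OLE stopping criteria cover shingles and other infections, but Appendix 6 has no stop for a severe infection such as pneumonia or sepsis

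*Protocol*

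**What the plan says.** Section 9.2.5 (Clinical Risks and Mitigation Strategy) lists the safeguards for moving from 14 days of dosing in the multiple-dose study to 18 months in the Core Study and 24 months in the OLE. One bullet, marked as revised under Amendment 07, covers stopping criteria in the "Core Study and OLE Phase based on skin rash, reoccurrence of herpes virus infections including any oral herpes, genital herpes or shingles, other infections", then MRI changes, ECGs and pregnancy. The bullet before it separates the phases for lymphocytes: subsets in the Core Study, absolute lymphocytes in the OLE.

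Section 9.3.3 introduces its list (a) to (j) with the words "Safety-related criteria for discontinuation of study drug during the Core Study include the following". Criterion (c) states "All subjects with severe infections will be discontinued from study drug" and "All subjects with herpes zoster (shingles) or ocular herpes infections will be discontinued from study drug, regardless of severity of presentation". The section closes with "Safety-related criteria for discontinuation of study drug during the OLE Phase are provided in" Appendix 6.

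Appendix 6 has seven criteria: (1) absolute lymphocyte count, (2) rash, (3) moderate to severe oral or genital herpes, (4) MRI findings, (5) pregnancy, (6) QTcF above 500 msec, and (7) a QTcF rise above 60 msec with QTcF above 450 msec. Item 2 covers "A subject with any skin rash of moderate to severe intensity, or any rash lasting more than 72 hours regardless of severity", as well as suspected drug rash, and excepts only oral and genital herpes. Appendix 6 also has a general provision: "The investigator may discontinue study drug or withdraw the subject from the study at any time for safety or administrative reasons".

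**The concern.** The risk section promises an infection-based stop in the OLE, and the operative list for the OLE does not contain one. An ethics committee or safety board reading 9.2.5 would believe the safeguard exists. An investigator with a subject who has severe pneumonia would look in Appendix 6 and find no rule.

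The matter is relevant to this drug. Section 7.2 reports clear falls in CD4, CD8 and CD19 counts at 200 and 400 mg, and evidence of some CD4 reduction at 50 to 100 mg by Day 15. The OLE dose is 50 mg for up to 24 months. Core Study placebo completers who enter the OLE receive the drug there for the first time, so excluding subjects who stopped drug in the Core Study says nothing about how they will tolerate it.

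**Working it through.** No arithmetic beyond counting is needed; the check compares the texts item by item.

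**Section 9.2.5 against Appendix 6**

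| Category in 9.2.5 (both phases) | OLE criterion in Appendix 6 | Match |
|---|---|---|
| Skin rash | Item 2 | Yes |
| Oral herpes | Item 3 (moderate to severe) | Yes |
| Genital herpes | Item 3 (moderate to severe) | Yes |
| Shingles | Not named; item 2 if the rash qualifies | Partial |
| Other infections | None beyond what items 2 and 3 catch | No |
| MRI changes | Item 4 | Yes |
| ECGs | Items 6 and 7 | Yes |
| Pregnancy | Item 5 | Yes |

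The count is 6 matched + 1 partial + 1 unmatched = 8. If the herpes types are taken as one heading, it is 4 matched (rash, MRI, ECG, pregnancy) + 1 partial (herpes) + 1 unmatched (other infections) = 6. Other infections is the unmatched entry either way.

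**Shingles.** Item 2 does not except zoster, so a moderate or severe zoster rash, or one lasting more than 72 hours, stops drug. The remainder is a mild rash of 72 hours or less, or zoster without rash. That gap is narrow.

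**Severe infection that is neither a qualifying rash nor oral or genital herpes, without confirmed lymphocytopenia**

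- *Core Study.* In Table 2 of Section 9.3.3 the severe-infection column requires discontinuation in the row below the discontinuation threshold, in the row between the threshold and the population-adjusted LLN, and in the row for "absolute counts always > population-adjusted LLN". That is 3 of 3 rows, so the stop does not depend on counts.
- *OLE.* Items 1 to 7 are not triggered, so 0 of 7 apply. The decision is left to the investigator's discretion.

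**Does the OLE lymphocyte rule fill the gap?** No. Item 1 acts on the count alone. A first confirmed lymphocytopenia leads to interruption, restart depends on recovery of the count with no condition on infection, and permanent discontinuation follows only a second confirmed occurrence within 6 months. In the Core Study, a subset count below threshold together with any infection means discontinuation.

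**Drafting history.** The preceding protocol version, also in the file, has a single bullet in 9.2.5 covering lymphocytes, rash, herpes and other infections without naming a phase. The Amendment 07 text splits it, gives the OLE its own lymphocyte basis, and places infections under both phases. Phase scope was therefore being addressed when infections were assigned to the OLE, though this does not show which of the two places is wrong.

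**The case against.** The strongest reply is that 9.2.5 is a rationale summary, Appendix 6 is the operative list, and a lighter OLE list may have been intended. Core criterion (i), any seizure, is also missing from Appendix 6; subset thresholds give way to absolute lymphocytes; and central dermatology review is dropped. On that reading the only error is one over-inclusive bullet. This is plausible and cannot be settled from the text, but it leaves 9.2.5 overstating the protection, so one of the two places must still change.

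A second reply is that severe infections are escalated in any case. Section 9.4.1 directs a discussion with the medical monitor about suspending drug for concurrent illness. Section 9.5.1.5.1 asks for detailed reports on zoster and severe infection. Pneumonia or sepsis that requires hospitalisation or threatens life is an SAE, reportable within 24 hours (9.5.1.5.2, 9.5.4.1). OLE entry also excludes active infection and low lymphocytes. All of this stands and limits the harm. However, the entry limits act only at Visit 21, and escalation is not a stopping criterion. That both lists are introduced as non-exhaustive does not help either, since the Core list is worded the same way and still spells out infections.

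Third, the risk should not be overstated. Section 9.4.4 reports no infections at 100 mg or below in the 14-day multiple-dose study and a lower exposure for the 50 mg fed tablet than for the 100 mg fasted capsule. Section 7.1 describes favourable interim safety at all doses. These points bear on weight and leave the contradiction in place.

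Fourth, discontinuation is permanent under 9.5.5, whereas suspension under 9.4.1 can be reversed. That is a real cost of adding the rule.

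**Conclusion.** The concern holds. Section 9.2.5 attributes to the OLE a stopping criterion for infections that Appendix 6 does not contain. The main gap is severe infection outside rash and oral or genital herpes: mandatory discontinuation in the Core Study at any subset count, and discretionary in the OLE for up to 24 months. The zoster gap is minor.

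The conclusion rests on reading Section 9.3.3 (a) to (j) as limited to the Core Study, which its heading and its pointer to Appendix 6 both support. The protocol gives no rate for such infections, so the number of subjects affected cannot be estimated. The inconsistency should be fixed; it does not undermine the study's analyses.

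**What to change.** Preferred: add two criteria to the Appendix 6 list. (1) Any subject with a severe infection discontinues study drug. (2) Any subject with herpes zoster discontinues study drug, whatever the severity. Ocular herpes can be carried over with (2) for consistency with Core criterion (c), although 9.2.5 does not name it. Neither rule uses subset counts, so sites can apply both even though OLE subset reports go to the sponsor only.

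Alternative, if the shorter OLE list was intended: reword the bullet in 9.2.5 so that shingles and other infections are listed for the Core Study only.

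Cost: two lines in Appendix 6, or one reworded bullet, by amendment with a letter to sites; no new procedures or samples. The first option is likely to mean a few more OLE discontinuations, which are permanent under Section 9.5.5 even if the infection resolves. The second leaves the stop for severe infection discretionary throughout the OLE.
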